11.3. Inclusion Criteria

- Documentation of symptomatic persistent AF
 - Defined as having a continuous episode lasting longer than 7 days but less than 6 months documented by consecutive ECG recordings
- OR

- Defined as having a continuous episode lasting longer than 7 days but less than 6 months documented by an ECG recording and one doctor note indicating patient had symptoms consistent with AF
- Failure or intolerance of at least one Class I or III antiarrhythmic drug
- Age 18 or older (or older than 18 if required by local law)

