13.7. Medications

It is recommended to discontinue the use of Class I and III antiarrhythmic medication by the end of the 90 day post-procedure blanking period. Up-titration of the dose is allowed only in the 90 day post-procedure blanking period.

Information regarding medications prescribed for anticoagulation or to treat atrial arrhythmias, including the medication name, purpose for use, start and stop dates, and route of administration, will be collected from subject enrollment through study exit.

13.7.1. Class I and III antiarrhythmic medication use after the 90 day post-procedure blanking period

- Subjects are allowed to remain on Class I or III antiarrhythmic medications at the historic maximum ineffective dose (on prior to the ablation procedure) after the 90 day post-procedure blanking period.
- Subjects may re-initiate, at any point during follow-up, a Class I or III antiarrhythmic medication that failed or was not tolerated prior to the ablation procedure at the same or lower dose.
- Initiation of a new Class I or III antiarrhythmic medication after the 90 day post-procedure blanking period will be treated as a primary endpoint failure.
- Remaining on a dose higher than the historic maximum ineffective dose (on prior to the ablation procedure) after the 90 day post-procedure blanking period will be treated as a primary endpoint failure.

All medications are permitted in the study with the exception of investigational drugs that may confound the study results.

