6.2.2.2. Endpoint Definition

Treatment success is defined as freedom from treatment failure. Treatment failure is defined as any of the following components:

- Acute procedural failure
- Documented AF/AT/ AFL on Holter/TTM/12-lead ECG after the 90 day blanking period
 - Minimum of 30 seconds on Holter/TTM and 10 seconds on 12-lead ECG
- A reablation for the treatment of recurrent AF/AT/AFL after the 90 day blanking period
- Class I or III antiarrhythmic drug (AAD) dose increase from the historic maximum ineffective dose (prior to the ablation procedure) or initiation of a new Class I or III AAD after the 90 day blanking period. Note: remaining on the same pre-ablation dose or decreased dose, or re-initiation of a previously failed or not tolerated Class I or III AAD after the 90 day blanking is not considered a failure. Subjects are allowed to remain on Class I or III antiarrhythmic medications at the historic maximum ineffective dose (on prior to the ablation procedure) after the 90 day post-procedure blanking period.
- Ablation using RF in the left atrium

Blanking period is defined as the first 90 days after the index ablation procedure. Recurrences of atrial arrhythmias during the blanking period will not be counted in the determination of the first clinical failure for the primary endpoint. Within the blanking period, recurrent arrhythmias can be managed with antiarrhythmic drugs, cardioversion or one cryo re-ablation procedure of the pulmonary veins. Titration of Class I and III antiarrhythmic medications are allowed during the blanking period.

Acute procedural failure is defined as:

- Inability to isolate all accessible targeted pulmonary veins (minimally assessed for entrance block and, where assessable, exit block) during the index procedure
- Left atrial non-PVI ablations including but not limited to, ablation of linear lesions, complex fractionated electrograms or non-PV triggers

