6.5. Adjustments for Multiple Comparisons

A Hommel multiple testing procedure will be utilized to maintain an overall type I error rate of 0.025 for the three hypotheses tested as part of the secondary objective³. Testing for this objective will be performed if the primary objectives are met. The Hommel procedure is a "step-up" method of error adjustment.

The three hypotheses associated with the secondary objective (see 6.2.3) will be denoted here as H(1), H(2), and H(3). H(1), H(2) and H(3) denote the null hypothesis for change in AFEQT, change in SF-12 mental component, and SF-12 physical component. For each of the hypotheses, p-values will be calculated and sorted $p(1) < p(2) < p(3)$. The decision rule to accept or reject each hypothesis will follow the step-up algorithm, where $\alpha=0.025$.

Step 1: If $p(3) > \alpha$, accept H(3) and go to Step 2, otherwise reject all hypotheses and stop

Step 2: If $p(2) > \alpha/2$, accept H(2) and go to Step 3, otherwise reject all remaining hypotheses and stop

Step 3: If (1) $\alpha/2 < p(2) \leq 2\alpha/3$ and $p(1) \leq \alpha/2$ or (2) $p(1) \leq \alpha/3$, reject H(1); otherwise accept H(1).

³ Hommel, G. A stagewise rejective multiple test procedure based on a modified Bonferroni test. *Biometrika* 1988; 75, 383-386.

Demographic strata with <5 events will be combined with other strata if the resulting combination is still deemed analytically meaningful, or may be ignored due to information sparsity. Age will be calculated as [year of baseline date – year of birth] as the case report form does not collect the exact date of birth for a subject. For subgroup analysis, age will be divided into quartiles. The log-rank test will be utilized. If the overall log-rank test of equality over strata is significant for strata with more than two levels, Tukey's range test will be used to adjust type I error for the comparison between multiple subgroups. Subgroup analyses will be performed in the same datasets in which the corresponding primary or secondary objectives are analyzed.

In addition to subgroup analyses by demographic variables, there are eight pre-specified subgroup analyses that will be performed:

- by Left Atrial Diameter (LAD) at the most recent measurement prior to the procedure;
- by duration of persistent AF, measured in terms of months prior to the procedure;
- by number of prior failed AAD's
- by history of hypertension (binary)
- by history of cardioversion (binary)

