- by Subjects with baseline ECG performed within 30 days of index ablation versus > 30 days.
- by body mass index (BMI) > 40 versus ≤ 40
- Major inclusion criteria: Subjects with symptomatic persistent AF documented by two documented ECGs versus subjects with symptomatic persistent AF documented by one ECG and a doctor note indicating the patient had symptoms consistent with AF

The last three subgroup analyses in the list above (by ECG within 30 days of baseline, by BMI > 40, and by major inclusion criteria documentation method) were added based on FDA's correspondence related to STOP Persistent AF IDE Study (G160177/S007) received by Medtronic on January 10, 2018. Each of these subgroups will be analyzed using nonparametric Kaplan-Meier methods like the demographic variables in the manner described above. LAD will be divided into quartiles, while divisions of prior persistent AF duration and prior failed AAD's into discrete bands will be determined after examination of the distribution of these variables in the data.

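### The subgroup analysis by number of prior failed antiarrhythmics appears to use an endpoint whose drug-failure rule itself depends on drug history, which tilts one component towards subjects with more failed drugs.

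*SAP*

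**What the plan says.** The SAP lists eight pre-specified subgroup analyses beyond the demographic ones. One is "by number of prior failed AAD's". On method it says "Each of these subgroups will be analyzed using nonparametric Kaplan-Meier methods like the demographic variables in the manner described above", and the test named there is the log-rank. On data it says "Subgroup analyses will be performed in the same datasets in which the corresponding primary or secondary objectives are analyzed". The bands are left open: the division of "prior failed AAD's into discrete bands will be determined after examination of the distribution of these variables in the data".

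The primary efficacy endpoint (SAP 6.2.2.2; the same in Protocol 6.2.1 and 17.3.1) has five failure components. The drug component counts "initiation of a new Class I or III AAD after the 90 day blanking period", or a dose above the historic ceiling. It then makes an exception: "re-initiation of a previously failed or not tolerated Class I or III AAD after the 90 day blanking is not considered a failure". Protocol 13.7.1 repeats the exception as a permission, limited to the same or a lower dose: "Subjects may re-initiate, at any point during follow-up, a Class I or III antiarrhythmic medication that failed or was not tolerated".

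Entry requires "Failure or intolerance of at least one Class I or III antiarrhythmic drug" (Protocol 11.3), so every eligible subject has at least one exempt drug.

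**The concern.** A log-rank comparison between strata asks whether the strata share one failure process. That reading needs failure to mean the same thing in each stratum. Here, whether a given drug start is a failure depends on the subject's own antiarrhythmic history, and the strata are defined by a count drawn from that history. None of the other seven listed variables (left atrial diameter, AF duration, hypertension, cardioversion, ECG timing, BMI, method of documenting AF) enters the failure definition.

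Take two subjects with the same rhythm course who start the same Class I drug on day 150. One failed that drug before ablation and is not a failure. The other never took it and is. If the first sits in a higher band, part of any difference between the curves comes from scoring, not from the effect of ablation. At stake is how a pre-specified subgroup result is read: a real disadvantage in subjects with several failed drugs could be partly masked, or a small apparent advantage could arise. Neither primary decision is affected.

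**Working it through.** **Plan figures.** The SAP gives no expected rate for the drug component and no expected subgroup difference, so there is no planned figure for this point to reproduce. The primary efficacy power does reproduce (exact binomial, 40% versus 54%: 66 of 135 gives alpha 0.0224 and power 0.899; 72 of 148 gives 0.0202 and 0.917), but it does not bear on this point.

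**Direction.** Fix a subject's behaviour after day 90 and vary only the history.

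1. Let E be the set of Class I or III drugs already failed or not tolerated. Restarting a drug in E within the dose limit is not a failure; starting one outside E is.
2. Adding a failed drug enlarges E. The starts that count as failure with the longer history are a subset of those that count with the shorter one.
3. So, with equal prescribing, the subject with more failed drugs cannot do worse on this component and may do better.
4. The stratifier counts failed drugs, while E also holds drugs that were not tolerated. The visible text does not say whether intolerance is counted as failure. If it is not, a subject with one failed and two not-tolerated drugs has a count of one and three exempt drugs. E therefore grows with the count on average, not exactly.

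**Size.** For 12-month success, only subjects whose sole failure by day 365 would be a drug start matter. An exempt subject who later has recorded AF/AT/AFL or a re-ablation fails anyway, though later, which can still shift the log-rank comparison somewhat.

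Assumptions, none from the documents unless stated:
- f = share of subjects whose only failure is a drug start, if every start counted; 2% to 15%
- M = 5 candidate Class I or III drugs, with choice independent of history
- k = number of exempt drugs: 1 in one group, 3 in the other
- success of 54% in both groups when every start counts (the SAP's planning rate, borrowed as an anchor)
- 75 subjects per group (half of 150)

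Success = 0.54 + f × k/M. Difference = f × (3 − 1)/5 = 0.4 f.

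| f | k = 1 | k = 3 | Difference | Chance of significance |
|---|---|---|---|---|
| 2% | 54.4% | 55.2% | 0.8 points | 3.1% |
| 5% | 55.0% | 57.0% | 2.0 points | 4.3% |
| 10% | 56.0% | 60.0% | 4.0 points | 7.1% |
| 15% | 57.0% | 63.0% | 6.0 points | 11.3% |

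The last column approximates the log-rank test by a comparison of two proportions at two-sided 0.05, in the direction favouring the three-drug group; with no artefact it would be 2.5%. The ceiling on the difference is f itself, reached only if no start in the low band is exempt and every start in the high band is. If every start counted, or none did, the difference in this illustration would be zero.

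**The case against.** **The text is incomplete.** The SAP's introduction places subgroup analyses in section 6.7, and the opening of that section is not in the text available. It may name the endpoint or carry a caveat. That stands: use of the primary efficacy endpoint is inferred from the Kaplan-Meier and log-rank methods and the reference to the corresponding objectives.

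**Most of the endpoint is unaffected.** Four of the five components ignore drug history. Monitoring is fairly dense (weekly and symptom-triggered transmissions after month 3, Holter at 6 and 12 months, ECG at visits), so a subject who needs a drug may already have a recorded failure. That also stands, and it is why the effect may be very small.

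**Stronger readings do not hold.** A reader might infer that each failed drug gives exactly one exempt drug. The exemption's wider wording and its dose limit prevent that. A reader might also count every drug start that precedes a recorded arrhythmia: if 10% to 20% of subjects start one, and it is new in 80% of the low band and 30% of the high band, the gap is 5 to 10 points (0.10 × 0.50 to 0.20 × 0.50). None of those inputs is in the documents, and the sum ignores exempt subjects who fail later on rhythm or re-ablation, so it is not a difference in 12-month success.

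**The primary endpoint is a defensible default for subgroups.** Agreed. The visible text attaches no hypothesis or success criterion to this one. That argues for adding a companion result, not for replacing the planned one.

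**Conclusion.** The point holds as a statement about the scoring rule: one component of the endpoint depends on the variable that defines these subgroups, and with equal prescribing it leans towards subjects with more failed drugs. It rests on the inference that the primary efficacy endpoint is the one used.

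The size cannot be derived from the documents. Roughly 1 to 6 points for one versus three exempt drugs follows from the assumed 2% to 15% drug-only failure share, five candidate drugs and history-blind drug choice. Because the bands are not fixed, the one-versus-three contrast is itself illustrative.

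A reader might infer that the more refractory subgroup will come out ahead. The documents do not support that. The lean is in the rule, and the observed difference could still go against that group. This is a low-cost improvement to the interpretation of one subgroup, not an error in the primary analysis.

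**What to change.** For this subgroup only, keep the planned analysis and add to the SAP:

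- **One companion analysis.** Repeat the Kaplan-Meier and log-rank comparison, in the same bands, with any Class I or III start or restart after day 90 scored as failure regardless of drug history. All other components stay as defined. Naming this single version in advance avoids a later choice between alternatives.
- **One table.** First failures by component in each band, which shows directly how many rest on a drug start.
- **One note.** The planned version is affected by the restart exemption.

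The cost is a few lines in the SAP, one extra run and one table. Protocol 13.7 already collects drug names with start and stop dates, so starts after day 90 can be identified without new data. There are two limits to state. The companion endpoint is not the primary endpoint, so its rates should not be compared with the 40% goal. It also does not count subjects who simply remain on a pre-ablation drug, so drug exposure is still not fully equalised across bands. The primary endpoint, the primary analyses and the clinical rules on drug use stay as they are.

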Kojodjojo P, et al Heart 2010;96(17):1379-1384. ^v	Prospective, consecutive patients	1	34	3M,6,12 and every 6 thereafter (24h Holter + ECG +symptomatic event recorder)	Any AF/AT > 30s	0.48 (0.30, 0.65)	YES	83%
Kubala M, et al Clin Electrophysiol 2011;34(7):837-843. ^{vi}	Prospective, consecutive patients, PVI-only	1	33	ECG and 24hr Holter @ 1M,3M,6M,12M and symptomatic event recorder	AF > 30s	0.52 (0.34, 0.69)	YES	Not reported

Medtronic Confidential

STOP Persistent AF Clinical Investigation Plan

Version 6.0, 01DEC2017 Page 68 of 128

Malmborg H, et al Europace 2013;15(11):1567-1573. ^{vii}	Prospective, randomized, PVI-only	1	15	ECG @ 3M,6,12 and 7 day Holter @ 6M,12M	AF > 30s	0.60 (0.32, 0.84)	NO	98%
Neumann T, et al J Am Coll Cardiol 2008;52(4):273-278 ^{viii}	Prospective, consecutive patients, PVI-only	3	53	7 day Holter @ 3M,6M,9M,12M	AF > 30s	0.42 (0.28, 0.56)	YES	97%
Schmidt M, et al Int J Cardiol 2013;167(1):114-120 ^{ix}	Consecutive patients, PVI-only	3	44	ECG and 72hr Holter @ 1M,3M,6M,9M,12M and symptomatic event recorder	AF or Flutter >30s	0.77 (0.62, 0.89)	YES	100%
Schmidt M, et al Clin Res Cardiol 2012;101(10):777-785. ^x	Prospective, consecutive patients, PVI-only	1	33	ECG and 72hr Holter @ 1M,3M,6M,9M,12M and symptomatic event recorder	AF > 30s	0.70 (0.51, 0.84)	NO	98.40%
Lemes C, et al Europace. 2015 May 19. [Epub ahead of print]. ^{xi}	Retrospective, PVI-only	2	49	Holter and ECG and telephonic interviews @ 3M,6M,12M	Any AF/AT > 30s	0.69 (0.57, 0.83)	YES	100%
Weighted average (weights based on study sample size)						59.3% (43.8, 74.4%)		

*Confidence interval calculated with binomial Fisher's exact methods

Medtronic Confidential

Sample Size Calculation

For the US/Canada/Europe cohort, 150 treated subjects affords 90% power based on the following assumptions:

- One analysis at 12-months
- 12-month efficacy rate = 54%
- OPC = 40% at 12-months
- Overall alpha = 0.025, one-sided
- 10% attrition through 12 months
- Binomial exact methods

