Table 12 summarizes the published literature of 12-month efficacy rates for Cryoballoon PVI ablation. The summary estimates 12-month efficacy to be 59.3%. Due to more stringent endpoint definition, increased monitoring, and the potential for publication bias, this study protocol assumes a 12 month efficacy rate of 54% for the sample size calculation. With 150 enrolled and treated subjects, minus an assumed 10% attrition rate, the expected number of subjects with 12 months of follow-up at the final analysis is 135.

For the US/Canada/Europe/Japan cohort, 165 treated subjects affords 92% power to test the primary endpoint based on the same assumptions. With 165 enrolled and treated subjects, minus an assumed 10% attrition rate, the expected number of subjects with 12 months of follow-up at the final analysis is 148.

Determination of Subjects/Data for Analysis

All enrolled subjects who have the Arctic Front Advance Cardiac CryoAblation Catheter inserted into vasculature will be included.

Sensitivity Analyses

A sensitivity analysis will be conducted to estimate the potential impact of subjects with less than 12 months of follow-up at the final analysis. The mortality rate in this patient population is anticipated to be low. The total assumed attrition rate through one year is 10%. Because the primary endpoint will be tested using survival methods, all treated subjects are included in the primary analysis, and therefore no subjects will have complete missing data. For subjects that exit early, a tipping point analysis will be conducted to estimate the potential impact of subjects with less than 12-months of follow-up. These subjects will be defined as subjects with partial data. The tipping point analysis methods will be as follows. For each subject with less than 12-months of follow-up, each subject will be set to treatment failure (failure date set to date of study exit). The 12-month Kaplan-Meier estimate will be re-calculated with the earliest (closest to index ablation) sequentially added to the Kaplan-Meier analysis, and the results presented in table format. The tipping point will be defined as the number of additional failures in which the 40% OPC is crossed by the lower 95% confidence bound.

Medtronic Confidential

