7.1. Sample Size Determination for Efficacy Endpoint

Sample size was estimated using Proc Power in SAS 9.4. The calculation was designed to find the number of analyzed subjects required for a one-sided exact binomial test ($\alpha = 0.025$) to have 90% power in declaring the event rate significantly greater than the efficacy performance goal of 40%, when in fact the true rate of treatment success at 12 months is 54%. Attrition from enrollment to 12-month follow-up was assumed to be 10%, implying $150 * (1 - 0.1) = 135$ and $\text{floor}(165 * (1 - 0.1)) = 148$ subjects analyzed at one year for the PMA-S and PMDA datasets, respectively. The sample size calculation under these conditions can be replicated with the following SAS code:

```
proc power;
  ods output=Power=Power;
  test = Binomial;
  alpha = 0.025;
  power = 0.9;
  ntotal = 135;
  ncrit = 66;
  actual = 0.54;
  alpha = 0.0224;
  power = 0.899;
  ntotal = 148;
  ncrit = 72;
  actual = 0.54;
  alpha = 0.0202;
  power = 0.917;
run;
```

	N Total	Upper Crit Val	Actual Alpha	Power
(PMA-S)	135	66	0.0224	0.899
(PMDA)	148	72	0.0202	0.917

[figure not shown]
The power calculation outlined above is based on the binomial test, which is conservative compared to the power provided by the Kaplan-Meier methods (described in 6.2.2) that will actually be used. In the case of Kaplan-Meier analysis, attrition is partial: data is included for all subjects up until they exit the study, so only subjects who exit prior to day 0 (index ablation) will provide no information to the analysis.

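### The readable SAP text tests quartiles of age and left atrial diameter with an unordered log-rank and leaves the AF-duration and failed-drug bands open without an outcome-blind rule; a trend test and a fixed banding rule would be a cheap improvement to these exploratory analyses

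*SAP*

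**What the plan says.** The subgroup text follows SAP section 6.5 in the copy read; SAP section 3 places subgroup analyses in section 6.7. On age it says: "For subgroup analysis, age will be divided into quartiles. The log-rank test will be utilized". Where a factor has more than two levels, one global comparison of all strata comes first, and Tukey's range test follows if it is significant. No trend test and no model with a continuous covariate is named in the readable text.

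Eight further subgroup factors are listed as pre-specified, to be handled in the same way as the demographic ones. Five are binary. The other three are ordered:

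- LAD, for which the rule is fixed in advance: "LAD will be divided into quartiles".
- Duration of persistent AF in months, with bands left open.
- Number of failed AADs, with bands left open.

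For the last two, division "into discrete bands will be determined after examination of the distribution of these variables in the data". The variables referred to are the covariates, not the outcomes.

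The same text lets demographic strata with fewer than five events be merged or dropped. The study is single-arm and unblinded (SAP section 5), and the sponsor's statisticians do the analysis (SAP section 6.2.1).

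**The concern.** There are two separate issues.

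**The test.** Age, LAD, AF duration and number of failed AADs are ordered. A log-rank test across four unordered groups spends three degrees of freedom and would give the same answer if the quartiles were shuffled. If the failure risk rises or falls steadily with the variable, a one-degree-of-freedom test uses the same events better. With fewer than 80 failures expected in either cohort, that matters for whether a moderate prognostic gradient is detected.

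**The bands.** Two of the eight subgroup factors described as pre-specified have no stated strata. Choosing bands from the covariate distribution is harmless in itself. In an unblinded single-arm study, however, the outcomes may be known to whoever makes the choice, and the readable text does not require otherwise. The rule on strata with few events shows that grouping can respond to event counts. A reader of the final report could not tell whether the bands were chosen independently of the results.

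What is at stake is how credible and informative the subgroup results are, not the success of the study.

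**Working it through.** **1. The plan's own figures.** The protocol (17.3.1) states that "150 treated subjects affords 90% power based on the following assumptions", with "Overall alpha = 0.025, one-sided". SAP section 7.1 uses an exact binomial test of 54% success against a goal of 40%. Taking the smallest critical count r with P(X ≥ r | n, 0.40) ≤ 0.025, then power P(X ≥ r | n, 0.54):

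- n = 135: r = 66, alpha 0.0224, power 0.899.
- n = 148: r = 72, alpha 0.0202, power 0.917.

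Both agree with the SAP. These are the nearest stated figures; no power, effect size or alpha is stated for any subgroup test.

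**2. Failures available.** With 54% success, 46% fail: 150 × 0.46 = 69; 135 × 0.46 ≈ 62; 165 × 0.46 ≈ 76. Simulating 150 subjects with 10% attrition gives about 66.

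**3. Formula.** Assumptions: log-linear effect, normally distributed covariate, two-sided 0.05. The noncentrality is λ = d × (ln HR)² × k, where d is the number of failures, HR is per SD, and k is the share of information kept:

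- Continuous Cox term, 1 df: k = 1.
- Trend over quartiles, 1 df: k = 0.856.
- Unordered quartiles, 3 df: k = 0.861.

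Power is the probability that a noncentral chi-square exceeds 3.84 (1 df) or 7.81 (3 df).

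Example, d = 69 and HR 1.35: (ln 1.35)² = 0.0901, so λ = 6.21 (continuous), 5.32 (trend) and 5.35 (unordered). Powers are 70.3%, 63.6% and 46.8%. The two quartile tests keep almost the same information, so the gap between them comes from the extra degrees of freedom.

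**4. Results, 69 failures** (losses in points, from unrounded powers)

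| HR per SD | Unordered, 3 df | Trend, 1 df | Continuous | Loss v trend | Loss v continuous |
|---|---|---|---|---|---|
| 1.10 | 8.4% | 11.3% | 12.4% | 3.0 | 4.1 |
| 1.20 | 19.0% | 28.9% | 32.8% | 9.8 | 13.8 |
| 1.25 | 27.1% | 40.3% | 45.8% | 13.2 | 18.7 |
| 1.30 | 36.6% | 52.3% | 58.7% | 15.7 | 22.1 |
| 1.35 | 46.8% | 63.6% | 70.3% | 16.7 | 23.5 |
| 1.40 | 57.0% | 73.4% | 79.8% | 16.4 | 22.8 |
| 1.50 | 75.0% | 87.6% | 92.0% | 12.6 | 17.1 |
| 1.60 | 87.4% | 95.1% | 97.4% | 7.7 | 10.0 |
| 1.75 | 96.5% | 99.0% | 99.6% | 2.6 | 3.2 |

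With 62 failures the largest losses are 16.7 (trend) and 23.4 (continuous); with 76 they are 16.8 and 23.4. At HR 1.5 and 76 failures they fall to 11.1 and 14.8.

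**5. Simulation check** (3,000 trials, 150 subjects, 54% success, 10% attrition; unordered / trend / continuous)

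- HR 1.3: 35.0 / 49.0 / 55.8%.
- HR 1.4: 56.1 / 72.6 / 79.6%.
- HR 1.5: 70.3 / 83.3 / 89.3%.
- No effect: 5.4 / 5.1 / 5.5%, so all three hold their level.
- Uniform covariate, HR 1.4: 57.9 / 75.2 / 78.1%.

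**6. Non-monotone effects** (same simulation, effect parameter 1.4)

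- Step at the top quartile: 54.9 / 52.0 / 51.2%.
- U-shape: 25.3 / 7.1 / 9.5%.

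Here the SAP's test is slightly better for the step and clearly better for the U-shape.

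**The case against.** The strongest reply is that the SAP deliberately chose non-parametric methods, and that choice has merits. It protects against step and U-shaped patterns, and a linear term can be nearly blind to a U-shape. This stands, and it is why the unordered test should be kept alongside rather than removed.

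Three stronger readings are tempting, but the documents do not support them.

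- A reader might infer that the plan simply loses 15 to 25 points of power. No subgroup effect size is stated, and the loss runs from about 3 points to about 23 with the assumed effect before changing sign for other shapes.
- A reader might infer that leaving the bands open inflates false positives. Picking the best of five ordinary bandings by p-value would give about 15% instead of 5%, and the best of 13 cut-points about 24%. Both figures assume selection by outcome. The SAP refers only to the covariate distribution, and choosing on that alone causes no inflation. Age and LAD are not exposed at all, since their quartile rule is fixed.
- A reader might infer that these are the study's only evidence on who benefits. The ancillary objectives are redacted, site and geography are examined separately (SAP section 6.3), and subgroup curves in a single arm show prognosis rather than benefit from treatment.

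Two further points also stand. The opening of the subgroup section is missing from the copy read, so a trend test or a statement of status there cannot be excluded. AF duration in months and a count of drugs may be heavily tied, which is a legitimate reason to look at their distributions before banding.

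**Conclusion.** The point holds as a cheap improvement to exploratory analyses; it is not an error. Under a monotone log-linear effect of about HR 1.25 to 1.5 per SD, with about 65 to 69 failures and two-sided 0.05, the unordered quartile test gives up about 12 to 17 points of power against a trend test on the same quartiles. Against a continuous Cox term it gives up about 17 to 24. The effect size, its shape and the significance level are assumptions of this check, not figures from the documents.

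The open bands for AF duration and failed AADs are a gap in documentation: the readable text does not ensure that they are set independently of outcome. It does not show that they will be set otherwise.

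The readable text attaches no success criterion to the subgroup results. Study success rests on the primary objectives (protocol section 7.2), so no primary or secondary conclusion changes.

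**What to change.** 1. For age, LAD, AF duration and number of failed AADs, name a 1-df log-rank trend test, or a Cox model with the variable continuous, as the lead subgroup test. Choose one and state it.
2. Keep the unordered log-rank and the Kaplan-Meier curves by band beside it, so that non-monotone patterns can still be seen.
3. Fix the AF-duration and failed-AAD bands by a rule that uses only the covariate, is set before outcomes are seen, and says how ties are handled. If the distributions must be inspected first, record that this was done without outcome data.
4. If the missing opening of the subgroup section already covers any of this, a cross-reference is enough.

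The cost is a few sentences in the SAP and one option in the same software, with no new data. The downside is one more exploratory p-value per variable, which should be labelled as such.
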